The proposed trial is guided by the Promoting Action on Research Implementation in Health Services (PARIHS) framework.⁴⁹⁻⁵⁵ The PARIHS framework and its three dimensions (context, facilitation, and evidence) was selected for addressing these barriers to implementation in AKI prevention.⁵⁴

C.2.a. Study Population: Site Inclusion and Exclusion Criteria. All patients at the participating sites will be enrolled into the trial with a series of inclusion and exclusion criteria.

VA Site Inclusion Criteria: All VA medical centers with a cardiac catheterization laboratory are eligible, and all catheterization operators at a site are included.. We currently have over-recruited 29 VA sites, but a minimum of 16 VA sites will be enrolled.

Patient Inclusion Criteria: Among these sites, only patients aged 18 or greater who undergo diagnostic coronary angiography or percutaneous coronary intervention (PCI or angioplasty) will be enrolled in the trial. CKD is of primary interest and it will be determined by a pre-existing CKD diagnosis in the VA medical record, or by two or more estimated glomerular filtration rates <60 (ml/min/1.73 m²) at least 90-days apart prior to presentation. **Patient Exclusion Criteria:** Patients with a history of dialysis (hemodialysis, peritoneal dialysis) or under the age of 18 will be excluded. Cardiac catheterization (also referred to as coronary angiography) is defined as a procedure in which a catheter is inserted into the femoral or radial artery and is threaded to the cardiac vasculature where radio-contrast dye is administered and a series of x-rays obtained in order to visualize the coronary arterial anatomy. PCI is when a clinical intervention is then performed to address any treatable pathology that is found.

C.2.b. Randomization. Randomization will occur at the hospital level in a 2x2 factorial design.⁴⁸ We will enroll a minimum of 16 Veteran Affairs (VA) hospitals with cardiac catheterization laboratories from across the United States (see Letters of Support and Facilities) that meet the medical center inclusion/exclusion criteria above. We will use a random number generator and block-randomize centers by the following variables: 1)

PROTOCOL

(Version #: 6, version date: 9-21-20)

VA region (1-4); and 2) patient volume (<800, 800+), see **Table 1** for the sites that initially met out inclusion/exclusion criteria.

C.2.c. Primary Endpoint. KDIGO AKI defined by ≥ 0.30 (mg/dL) or $\geq 50\%$ increase in serum creatinine over baseline within 48-hours of the procedure or within 7-days for in-patients, or onset of dialysis within 7-days.¹³

C.2.d. Data Collection and Data Coordinating Center. We have experience in using existing electronic health record (ViSTA, CPRS) and CART program quality initiative data collection to capture all patient and procedural characteristics, comorbidities, and outcomes in order to identify patients for pre-existing CKD, ascertain AKI outcomes, and to provide the data infrastructure to support the ASR intervention. In order to conduct national risk-adjusted surveillance for participating sites, we will collect data for the first 6 months after study approval at, in each of the 76 VA institutions with cardiac catheterizations laboratories.¹⁴ The CART data is collected through a structured data entry tool in the EHR. As part of a prior research project (VA HSR&D IIR 11-292), we have established a comprehensive automated data center with weekly feeds from CART and daily to weekly feeds from the data domains in the VA Corporate Database Warehouse (CDW), which extract data from the production EHR. For those few data sources with a delay more than a week, we have a supplemental automated tool that uses a VA approved interface layer to extract the data in near-real time from the production EHR. These data are transformed and merged through a validated process into an analytic data cube that can be analyzed to provide reports to operators and hospitals as well as providing data for review. A summary of the currently available data elements from the CART-CL clinical registry and EHR are shown in **Appendix 1**. Individual clinical registry elements conform to the American College of Cardiology National Clinical Data Repository data element definitions.⁵⁶ The research team, including the director of CART (CART Letter), has a long history of utilizing these data sources for research.

Due to the 2020 COVID-19 pandemic, many of our enrolled VA site cardiac catheterization laboratories have been temporarily closed or procedures have been greatly reduced. Disruption to normal laboratory procedures could impact the IMPROVE AKI study findings. Therefore, our research team is requesting access the COVID-19 Shared Data Resource in VINCI, containing information relevant to COVID-19 inside and outside the VA.

We will be using the COVID Shared data resource to identify overall rates of testing and COVID positivity at each site that has a cath lab to get a sense of COVID impact at that site. We will also be linking each of the cath patients to COVID testing status to get a sense of how often they were tested, and how many were cath'ed and COVID+. Lastly, we will assess whether COVID+ status had enough patients amonth cath patients to warrant inclusion as a risk factor, since AKI is a risk factor from covid. We will not be

Table 1. VA Site Characteristics		
Site	Region	Procedure Volume
554	1	1131
691	1	807
605	1	545
654	1	292
580	2	1794
549	2	1605
671	2	1015
537	2	629
586	2	341
626	3	1621
637	3	692
672	3	632
544	3	335
528*	4	1617
512	4	326
693	4	266
632	4	49

*2 sites

PROTOCOL

(Version #: 6, version date: 9-21-20)

analyzing any case level data from non-cath patients, but will use the COVID shared resource to aggregate as above.

C.3. AKI Prevention Toolkit. *Intervention:* All sites will receive the AKI Prevention Toolkit (**Appendix 1**) including 3 core interventions: 1. Standardized order sets; 2. IV and oral fluids; and 3. Reduced contrast volume. The interventions adhere to the KDIGO guidelines¹³ and add interventions developed and tested in our pilot intervention to implement AKI preventive strategies.^{1,3} We will also educate the sites on the hemodynamic guided fluid administration for volume expansion guidelines and PRESERVE results when released.^{57,58}

C.4. Virtual Learning Collaborative (VLC). *Intervention:* The VLC will be offered to eight teams (minimum of 4 with ASR, minimum of 4 without ASR) and will receive the AKI Prevention Toolkit.^{1,3} Each participating site will be supported to establish a multidisciplinary team charged with continuously improving AKI, which will include interventional cardiologists, cardiac catheterization lab manager and technicians, nursing representatives from the intensive care unit and/or holding areas, cardiology administration, nephrology, and representation from the quality improvement department (VA Clinical Application Coordinator [CAC] and Systems Redesign). Each VLC site team will be assigned 2 expert coaches from White River Junction VA (VA affiliate of Dartmouth): AKI quality improvement specialist and VLC and improvement specialist. A 60-minute VLC training call will be held monthly during the trial. The VLC and VLC+ASR will be coached independently to avoid contamination. All VLC sessions will be conducted using VA Microsoft Teams Meeting and recorded. VLC clusters will have access to shared team materials on VA including, AKI Prevention Toolkit, VLC session recording, uploaded homework from sites (which may include aggregated data on AKI and other factors over time), educational materials, and other tools or documents to support the VLC interventions.

Each of the sites in the VLC intervention will follow the same structure each month (see **Figure 4. VLC monthly calendar**). On the first of the month, teams will be required to submit homework to “VA VLC O365/ SPO Sharepoint folder,” a web-based platform that allows multiple users to access and upload files to be shared among approved members. The monthly homework will ask teams to share about the changes made during the previous month, including a review of successes and challenges. Expert team coaches will review the uploaded homework and provide team-based feedback. There will be a monthly learning lesson call. Each learning session call will consist of several key components: introduction and roll call, review AKI Prevention Toolkit components, process changes or quality improvement methodology, team sharing and/or reports on their work during the previous month. Coaches will be available via phone and email to answer any questions from teams, if requested. See **Table 2** for a description of VLC

Figure 4. Virtual Learning Collaborative Monthly Calendar

Week	Activities to be completed
1	Monthly Report Due to Coach 1 st of the month (or first workday of the month)
2	Coaches review team-based reports and send feedback to teams
3	Monthly Virtual Learning Collaborative session
4	Coaches available to teams by phone, email, or Adobe Connect as needed

PROTOCOL

(Version #: 6, version date: 9-21-20)

and TA call topics, which may be modified based on need. Participation will be measured by activity on the monthly calls, simple progress reports, and participation.

Table 2. Virtual Learning Collaborative and Technical Assistance Call Topics

Month	Clinical Topic	Quality Improvement Implementation Component
1	Getting Started team members/roles Project timeline Overview of bundle interventions from the AKI Prevention Toolkit	Components of a learning collaborative Problem identification Model for improvement Setting Global and Specific Aim Statements
2	Intervention 1: Standardize Pre- and Post-Cath Orders	Planning Process improvements (Process Maps/Flowcharts) What is the problem? What process will you focus on? What is the current process?
3	Intervention 2: IV and Oral Fluid Orders	Effective Communication
4	Intervention 3: Reducing contrast volume	Causation Fishbone diagrams
5	Intervention 2 continued NPO status	Change ideas Plan Do Study Act (PDSAs)
6	Intervention 2 continued Patient oral fluids	Measurement Process changes and outcome measures
7	Review Pre-PC interventions lessons learned Case 1-2	Lessons learned from interventions 1-4
8	Intervention 2 continued LVEDP matched hydration	Measures use of playbooks
9	Intervention 2 continued Delay Cath if IV fluid bolus not received	Ladder of inference
10	Review of Peri-Cath interventions trialed case study lessons learned	Lessons learned from interventions 5-6
11	Intervention 1 Standardize Pre- and Post-Cath Orders - revisit	Accomplishment: What is going well or be improved?
12	Intervention 2 and 3 IV and Oral Fluids and Reducing Contrast -revisit	Revisit improvement methods
13	Review of interventions trialed lessons learned Case 3-5	Lessons learned from interventions 7-8
14	Review of Process Changes implemented	Planning for sustainability PDSA/SDSA
15	How to sustain and spread changes in practice	NHS Sustainability Model
16	Sustainability/Spread NHS Model for Sustainability	NHS Sustainability Model
17-18	Final Team Reports and Plans for next 18 months post-intervention	Lessons Learned

Evaluation and Measurement: Process measures will be self-reported by participating teams each month in a monthly homework or report identifying the process changes made during the previous month including the bundle interventions implemented during the previous month. Process measure collection will be duplicated by existing field-defined data elements captured by the Data Coordinating Center for which our research team has extensive experience. The report will also ask teams to submit the team meeting agenda and minutes. Process measures are reported in **Table 3**. To supplement these reports, each team champion(s) (current directors of catheterization laboratories) will be tasked with giving a 4-5-minute report on their progress on each VLC call. Based on our pilot, the key process changes to be measured are the use of AKI prevention toolkit, clinical champions, empowered nurses, team

Table 3. VLC and TA Evaluation and Measures

Process changes (measured by EMR and collected by sites)	# bundle interventions implemented 
 - Standardized order sets - IV fluids - NPO status (reduced to 2 hours) - Patient oral hydration - Reduced contrast volume - LVEDP matched hydration - Delay case if IV fluid bolus not received # of process changes made, agenda, minutes
Process measures (measured by EMR and collected by sites)	
 1. NPO duration (hours) 2. Total oral fluid last 24 hours (mL) 3. IV fluids ordered prior to procedure (order volume in mL) 4. Total IV fluids last 24 hours (mL) 5. IV fluid bolus given (500+ mL 1-hour prior to procedure) (yes/no) 6. IV at keep vein open (KVO)? 7. IV Pump used? 8. Procedure delayed for IV fluid bolus (yes/no) 9. Calculated MACD (5mL x body weight in kg over base line serum creatinine) 10. Calculated CrC :Contrast Ratio (3x CrC) 11. Left Ventricular End Diastolic Pressure 12. Contrast volume
Outcome	Acute Kidney Injury
Fidelity measures: VLC or TA	
VLC: Adherence to VLC key components:
 
 - participation on the monthly learning calls (verbal, chat box entries) - submitted homework or reports - active participation in learning community - team huddles outside of LC 
TA: Adherence to TA components:
 
 - attendance and participation on monthly technical assistance calls - team initiated contact
Interviews every 6 months	Improvement training Improvement efforts Implementation barriers and successes

PROTOCOL

(Version #: 6, version date: 9-21-20)

champions, protected time for team meetings, and QI training.³ A survey will be completed monthly for each team following each call or session through VA RedCap.

C.5. Technical Assistance (TA). *Intervention:* TA will be offered to the eight teams randomized to the TA condition (minimum of 4 ASR, minimum of 4 without ASR) and will receive the AKI Prevention Toolkit.^{1, 3} TA will have monthly scheduled TA calls (60 minutes each) with each team individually to review and discuss the bundle interventions (as is done in the VLC group) and allow for a consultation with experts on the AKI bundle interventions. TA calls will be driven by an agenda with timely topics used to assess where sites are at with implementing the AKI Prevention Toolkit led by the AKI improvement specialist ([name], External Collaborator). All TA calls will be conducted with individual hospitals in each cluster (TA, TA+ASR). The goal of the TA consultation call is to address questions, review progress, and discuss challenges for the sites in implementing the AKI Prevention Toolkit. TA sites are also allowed to raise issues or concerns for discussion. If additional expertise is needed for specific questions, the TA expert will either schedule a follow-up call or respond via email. Teams are allowed to reach out to the TA expert at any point during the 36 months. TA will follow Call Topics in **Table 2**. Fidelity to the TA intervention and semi-structured interviews will be conducted as described in the VLC methods. TA will have the same touch points as VLC. All TA sessions will be conducted using VA Microsoft Teams Meeting and recorded. A survey will be completed monthly for each team following each call or session through VA RedCap.

Evaluation and Measurement: The process changes and primary outcomes (AKI) will be the same as those teams in the VLC (see **Table 3**. VLC and TA Evaluation and Measures). Fidelity measures for TA will include individual attendance at the 4 scheduled calls and team initiated contacts (see Appendix 1). Semi-structured phone-based interviews will also be conducted every 6 months for 18 months with TA team members to learn about improvement training, efforts, and implementation barriers and successes (see VLC methods).

PROTOCOL

(Version #: 6, version date: 9-21-20)

C.6. Automated Surveillance Reporting (ASR). *Intervention:* ASR will be offered to eight teams (4 with VLS, 4 with TA) as noted above in block randomization.^{1,3} The surveillance tools will execute a weekly updated estimation of each site's risk-adjusted performance, which generates a set of data that will populate series of tables and graphs for each site. There will be 3 levels of granularity (**Figure 5A**): 1) National Risk-Adjusted Ranking (**Figure 5B**) that reports the overall performance of each site relative to the national expectation, 2) Site Specific Performance Summary (**Figure 5C**) which highlights whether the site is out of expectation with regards to the statistical process control based methods used for sequential surveillance, and 3) patient list, which provides a table of the patients, with columns for each of the risk factors in the risk adjustment model and the predicted risk for the outcome and observed outcome (**Figure 5D**).

The figures and graphs will be placed inside a PDF directly along with text describing the methods used in the analysis, and an attached excel sheet of the 3rd level patient list report, which includes demographics, risk variables used in risk adjustment, the predicted risk of the outcome, and the observed outcome value for each patient at that site. The same data and format will be populated within a website with an identical workflow (**Figure 5**) and visualization to the PDF that users can log in and review the current and historical data of their site and all other catheterization sites within the VA intranet at any time. Only those sites randomized to receiving ASR (n=8) will be able to access the dashboard or receive the PDF's vial email link. This type of internally 'public' reporting has been shown in prior literature to potentially be more impactful than de-identified reporting, and we have the CART approval to operationalize the ASR reporting.

[figure not shown]

Figure 5. (A) Overview of the ASR workflow and examples of the available tables and graphs. (B) LEVEL 1: Overall risk-adjusted observed/expected ratio values over all 5 study years for each VA cardiac catheterization center. (C) LEVEL 2: RA-SPRT surveillance for Site C, which is noted to be above risk expectation, for alpha and beta errors of 0.10 and an odds ratio of 2.0 risk adjusted as noted previously. (D) LEVEL 3: Dashboard view of synthetic patient list for Site C that includes overview data as well as values for risk variables used in risk adjustment (additional variables not shown).

PROTOCOL

(Version #: 6, version date: 9-21-20)

Within either the web or excel-embedded-in-PDF user interface, users will be able to review patient data from their site to see which patients experienced the AKI outcome and to explore the analytic data for which factors were most likely related to AKI. This allows users maximal flexibility to inform their site-specific quality improvement initiative. Lastly, should a deeper chart review be desired, patient identifiers are available in the Level 2 Patient List portion of the tool to allow a user to open the EHR to conduct a deeper review and/or conduct other activities as part of their QI initiative protocols. Within the analytics module, the risk prediction models for post-procedural AKI will be developed monthly using the risk-adjusted sequential probability ratio test analysis method testing an odds ratio of 2.0 with a type I error of 0.05 and a type II error of 0.10, and a retrospective rolling 1 year window prior to the current month using the LASSO variable selection method applied to all candidate variables included in our previously published national risk model development work.⁵⁹ LASSO is conservative in its variable selection; unlike Ridge regression which merely shrinks coefficients LASSO pushes coefficients of weaker predictors to 0. The rolling window allows for continuous risk model recalibration, which is considered best practice for the use of risk prediction models due to calibration drift over time. For each model, discrimination (measured by the AUC) and calibration (by Cox intercept and slope) will be calculated and reported.^{60, 61}

Evaluation and Measurement: As noted above, the primary endpoint of AKI following cardiac catheterization will be assessed within the 2x2 study design. A number of process measures will be assessed as secondary endpoints, in a similar pattern to those reported for the VLC intervention. A survey will be administered monthly to each team with access to the ASR through VA RedCap as required progress reports prior to each monthly session (**Appendix 4**): whether they felt the information provided by risk-adjusted performance ratings was useful, whether access to the patient reviewer dashboard tool was helpful, and whether it influenced the implementation process during that month. Other characteristics will be captured through website logging and PDF report download usage statistics, which is tied to user authentication/direct download URL and will allow tracking of how often users and sites access the information and which parts of the report are viewed and utilized. We will analyze whether the use of the ASR increases or decreases over the course of the study and whether the use is different between the TA and VLC sites that have access to the ASR. To ensure that we capture the key process changes, team champions will submit responses to the mandatory monthly questionnaire for ASR (**Appendix 4**). A survey will be completed monthly for each team following each call or session through VA RedCap.

C.7. Statistical Analysis. We will conduct a 2x2 factorial analysis using a two-level hierarchical model that adjusts for observed patient covariates included in our VA AKI pre-procedural risk model and accounts for the clustering of patients within hospitals in comparing the effects of the four interventions comprising VLC, TA, and ASR on AKI.¹⁴ Adjusting for patient case-mix accounts for differences in the distribution of patient covariates across intervention groups, thereby removing chance confounding in the sample (randomization implies that the expected confounding is 0), and yields more

PROTOCOL

(Version #: 6, version date: 9-21-20)

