The risks involved in the participation in this study are very minimal and are outweighed by the potential benefits. There is no physical testing or additional laboratory testing involved beyond routine care. Only standard clinical practice will be implemented with improvements to that practice. No research interventions or tests will be conducted, only team-based interventions and automated reports to operators for the continuous improvement of routine care. Patients without a post-procedural laboratory completed for serum creatinine at the time of discharge will be sent home with laboratory orders (slips) for completion at 48 hours. Post-procedure laboratory measurement of serum creatinine is routine safe and effective care for patients with pre-existing CKD as the development of AKI is associated with a higher risk of short- and long-term mortality and renal failure.

F.1 Recruitment and Informed Consent

F.1.1. Recruitment Strategy

All VA Medical Centers have been recruited for the study and agreed to randomization. All patients meeting eligibility criteria will be enrolled in the study. Therefore, patient recruitment will not be performed at each site. Data on all cardiac catheterization patients will be pulled to the data core. Patient eligibility will be determined both at each VA site and by the data core. Each site will ensure data fields are populated and follow-up serum creatinine is measured. The data core will determine eligibility and populate analytic datasets for both bi-weekly automated surveillance reports and for the final statistical analysis of the study.

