2020

IMPROVE AKI Cluster- Randomized Trial (IMPROVE-AKI)

NCT03556293

09-21-2020

Statistical Analysis

We estimated the effect of both the implementation strategy and information support interventions, as well as their interaction, using hierarchical logistic regression models for 7-day postprocedural AKI. Models were fit using patient-level data with and without adjustment for the 20 patient-level characteristics in the VA-derived AKI risk prediction model underlying the Surveillance dashboard.²³ To account for site-level variation, observations were clustered at the site level, and models included a site-level random effect and controlled for site baseline risk-adjusted performance (observed to expected outcome ratio) in the 12 months before the study period. The decision to adjust for site baseline risk adjusted performance and other patient characteristics was prespecified. We implemented Satterthwaite small-sample correction because of the small number of clusters. Interim analyses and stopping criteria were not performed when determining sample size. In all models, the key features of interest were the interaction between implementation strategy and information support interventions, as well as differences across the four intervention combinations, with Assistance specified as the reference intervention. We estimated odds ratios (ORs) and 95% confidence intervals for pairwise comparisons of each combination of interventions and applied the Bonferroni correction for multiple comparisons. Analyses were run for the entire population and separately within the CKD subset. Corresponding sensitivity analyses modeled 30-day postprocedural AKI. Analyses were conducted using R 4.1.2.²⁶

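### Only ASR hospitals are shown the risk factors that the adjusted model conditions on, so fuller risk recording there could bias the ASR contrasts toward benefit, and no planned check would identify it

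*Protocol*

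**What the plan says.** **Who sees the risk model.** Protocol C.6 restricts the reports: "Only those sites randomized to receiving ASR (n=8) will be able to access the dashboard" or receive the PDF. The third reporting level is a patient list with "columns for each of the risk factors in the risk adjustment model and the predicted risk for the outcome and observed outcome". C.6 adds that patient identifiers let users open the chart, and that sites are ranked by risk-adjusted performance in a form visible to the other ASR sites.

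**What the analysis conditions on.** Protocol C.7 uses a model that "adjusts for observed patient covariates included in our VA AKI pre-procedural risk model". The SAP identifies the covariates as the "20 patient-level characteristics in the VA-derived AKI risk prediction model underlying the Surveillance dashboard". C.7 justifies adjustment as removing chance imbalance, on the ground that "randomization implies that the expected confounding is 0".

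**Where the covariates come from.** C.2.d describes a structured entry tool in the health record plus automated warehouse feeds. The Aim 3 statistical analysis (C.23) describes the covariates of the earlier aims as demographics, laboratory tests, medication administrations and conditions built from administrative codes. F.1.1 says of all sites: "Each site will ensure data fields are populated and follow-up serum creatinine is measured".

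**What protection exists.** The SAP fits each model with and without patient adjustment, controls for each site's observed-to-expected ratio in the 12 months before the study, and applies Bonferroni correction to pairwise comparisons. C.7 adds propensity weighting as a sensitivity analysis.

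**The concern.** Randomisation balances true case-mix in expectation. It does not balance recorded case-mix once one set of hospitals is shown, patient by patient, how each recorded factor moves predicted risk. If those hospitals then record comorbidity more completely, their patients look sicker on paper, expected AKI rises, and unchanged observed AKI looks like an improvement. The covariate has become partly a consequence of ASR, and conditioning on it carries that consequence into the ASR estimate.

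The protocol itself describes surveillance leading to better risk capture. In A.4, an outlier signal led to chart review, then to an unmodelled risk factor, and later to a new registry variable.

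At stake are the ASR main effect and every pairwise comparison of an ASR arm with a non-ASR arm, including VLC+ASR against VLC. The pre-study observed-to-expected ratio cannot register a shift that starts after the study begins. Propensity weighting, if built on the same recorded characteristics, would inherit it.

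**Working it through.** **1. The plan's own figures.** Inputs from C.11: 2,644 patients per arm, 661 per hospital, ICC 0.0009, AKI 0.27 against 0.2025.

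- Design effect = 1 + (661 − 1) × 0.0009 = 1.594. Effective n per arm = 2,644 / 1.594 = 1,658.7.
- Within one ASR level, two-sided 0.05: (0.0675 − 1.96 × 0.01475) / 0.01470 = 2.62, so power is 0.996 (stated: above 99%).
- At 0.05/6, power is 0.974 (stated: above 97%).

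Both reproduce without covariates, so the stated power does not rely on adjustment.

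**2. Which contrasts are affected.** Let b_TA and b_VLC be the spurious log odds ratios that recoding adds in the TA+ASR and VLC+ASR arms. In model (1) of C.7, the ASR coefficient is biased by b_TA and the interaction by b_VLC − b_TA. With equal recoding the interaction bias is zero. Of the six pairwise comparisons, four cross ASR levels and carry the bias. The other two (VLC against TA, and VLC+ASR against TA+ASR) do not.

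**3. Size under stated assumptions.** The documents give no recording rates, so these inputs are assumed: no true ASR effect, AKI 27%, five independent binary factors with prevalence 35% and odds ratio 1.8 each, and 70% of true cases recorded at non-ASR hospitals. I fitted the logistic model to the expected data, with ASR and the recorded factors as covariates. Standard errors use the effective sample sizes above (2 × 1,658.7 = 3,317.4 per side for the main effect). Rejection probability comes from a t test on 12 df with non-centrality |log OR| / SE. Critical values are 2.179 at 0.05 and 3.153 at 0.05/6.

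| Recorded at ASR sites | Adjusted ASR OR | log OR | SE, main effect | Rejects, main effect at 0.05 | SE, pairwise | Rejects, pairwise at 0.05/6 |
|---|---|---|---|---|---|---|
| 75% | 0.96 | −0.045 | 0.057 | 11% | 0.080 | 2% |
| 80% | 0.91 | −0.092 | 0.057 | 32% | 0.081 | 5% |
| 85% | 0.87 | −0.140 | 0.057 | 61% | 0.081 | 13% |
| 90% | 0.83 | −0.190 | 0.058 | 85% | 0.082 | 26% |

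The unadjusted OR is 1.00 in every row. The nominal pairwise rate is 0.05/6 = 0.8%.

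On the risk scale, the last row (OR 0.827 before rounding) is 0.27/0.73 × 0.827 = 0.306 in odds, or 0.234 in risk. That is a spurious reduction of about 0.036 against the planned 0.0675.

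**4. Milder cases.** If only one of the five factors moves, from 70% to 80%, the OR is 0.98 and the main-effect rejection rate is 6%. With other inputs (prevalence 30%, recording rising from 80% to 90%), the OR runs from 0.988 for one factor of odds ratio 1.5 to 0.903 for five of odds ratio 2.0. Over-coding acts the same way: specificity falling from 1.00 to 0.95 over that range of factors gives 0.988 to 0.899.

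**The case against.** Several objections carry weight.

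- **No recoding is documented.** Demographics and laboratory values cannot be improved by fuller coding. The 20 characteristics are not listed, and no section says that the staff who see the dashboard assign the administrative codes. The F.1.1 sentence covers sites in every arm. This stands: the documents support a route for bias, not its presence or size.
- **The SAP already fits an unadjusted model.** A divergence would be visible, and the SAP says that the decision to adjust was prespecified. This stands in part. Nothing says the unadjusted fit serves as a check on recording, or what follows if the two disagree. With 16 hospitals, divergence could also reflect true case-mix imbalance.
- **The patient list may not apply.** G.1.3.II and the Medical Record Review section describe the surveillance reports as de-identified and aggregate only, which contradicts C.6. If the aggregate description held, the mechanism would weaken.

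A reader might go further in three directions that the documents do not support. One is that coding alone would produce a spurious interaction. Both ASR arms see the dashboard, so that needs unequal recoding between them. Another is that the main-effect false-positive rates apply to the planned pairwise tests. Those tests are Bonferroni-corrected, and the rates are far lower. The third is that the unadjusted comparison is immune everywhere. In the CKD subset it is not, because C.2.a lets CKD rest on a recorded diagnosis, so recoding can change who enters the subset.

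**Conclusion.** The point holds as a conditional one. Exposure to the risk-factor list differs by arm, the same factors enter the adjusted model, they are recorded after randomisation, and no planned analysis is designed to separate a recording shift from an ASR effect. Fuller recording or over-coding of codable factors at ASR hospitals would push the adjusted ASR main effect and the four cross-level pairwise contrasts toward benefit for ASR.

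The size is unknown. The odds ratios of 0.96 to 0.83 require five factors to shift together from an assumed 70% baseline. A modest shift in one factor is negligible. The rejection rates also rest on the planned ICC of 0.0009. A larger ICC would lower them but would not remove the bias in the odds ratio.

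This does not justify discarding the prespecified 20-covariate model. Limiting diagnoses to those dated before 7/1/2018, for example, would count later-diagnosed disease as absent. It does justify a required check before an ASR benefit is claimed.

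**What to change.** Keep the 20-covariate model and add the following to the SAP:

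1. **A recording table.** By arm, for the baseline year and the trial period, report catheterization volume, the proportion classified as CKD, and mean predicted risk under coefficients frozen before 7/1/2018. A gap already present at baseline points to true case-mix. A gap that opens only in the ASR arms after the start points to a shift in recording or patient selection.
2. **A restricted sensitivity model.** Use the baseline observed-to-expected ratio plus only age, sex and laboratory-feed values, and report it beside the unadjusted model already planned. Repeat the CKD analysis with CKD defined by eGFR alone.
3. **A decision rule.** Claim an ASR benefit only if the adjusted, restricted and unadjusted estimates agree in direction and approximate size. Compare them as standardised risk differences, because a covariate-adjusted odds ratio can lie further from 1 than an unadjusted one without any bias.

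Separately, reconcile C.6 (patient list with identifiers) with G.1.3.II and Medical Record Review (de-identified, aggregate reports).

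The cost is SAP wording, one table and a few extra model fits on data already held. The downside is a more cautious ASR conclusion if the models diverge, including when the divergence is due to chance.
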